For the purposes of this study, the period of observation for collection of AEs extends from the time the patient gives informed consent through Week 26 (or early discontinuation visit). Follow-up of the AE is required until the event resolves or stabilizes at a level acceptable to the Investigator.

Intensity of Adverse Event

The intensity of the AE will be judged based on the following:

Mild	Awareness of sign(s) or symptom(s) which is/are easily tolerated
Moderate	Enough discomfort to cause interference with usual activity
Severe	Incapacitating or causing inability to work or to perform usual activities

Infusion Stopping Rules

Infusion will be stopped when:

- Allergic reaction is aroused after the product has been administered intravenously.
- Patient verbally decline the treatment at any moment prior, or during the infusion.

- Hyperpyrexia develops after infusion administration begins (core body temperature greater than or equal to 40°C) [57].
- PI may stop the study at any time, based upon PI's discretion
- Malignant Hypertension (180/120 mm/Hg)
- Sudden Severe Hypotension (30-40 mm/Hg drop from pre-infusion level)

Study Alteration Rules

If any of the following events listed below occur, administration of the study drug will be immediately suspended. The Internal Monitoring Committee (IMC), presided by the Medical Monitor will meet to review the incident and its etiology. The committee determine if it is likely related to the drug, the infusion or unrelated. If the IMC along with the Medical Monitor agree that the SAE is unlikely or unrelated to the drug, the study will be continued. If the SAE appears to be definitely drug-related, the study will be stopped. If the SAE is probably or possibly linked to the drug, the IMC will determine the risk to future patients and decide if the study should proceed or be stopped.

Study Stopping Rules

The stopping rules listed below will trigger cessation of enrollment and potential study closure pending a comprehensive DSMB safety review.

1. Any infusion related death, deemed by PI to be associated or possibly associated with study drug.
2. Three or more of the same Grade 3 or higher AEs (judged by the investigator, medical monitor or sponsor), including infusion site reactions.
3. Any event which, in the opinion of the investigator, medical monitor or sponsor, contraindicates further dosing of additional subjects.

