1. INTRODUCTION

The purpose of this Statistical Analysis Plan (SAP) is to describe the analyses to be included in the Clinical Study Report for Protocol HBCOVID-01. Details of the planned final analysis provided.

Additional detail with regards to data handling conversions and the specification of the data displays will be provided in the Programming Specifications (PS) document.

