5.3.2.1. Adverse Events

AEs will be coded using the most recent version of the Medical Dictionary for Regulatory Activities (MedDRA).

A treatment emergent adverse event (TEAE) is defined as an event that has onset date on or after the first day of exposure to infusion treatment and on or before the last day of infusion treatment. Here the first day of exposure is defined as the first day of exposure to infusion treatment.

Treatment Adverse events (TAES) are summarised descriptively, whereas non-TEAEs are presented in listings. TAE data will be displayed in terms of the number of subjects with at least one event (N), percentage of subjects with at least one event (%) and the number of events (E).

Individual adverse events will be listed.

The details of the planned displays are in programming specification document.

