7.1.3. Prior and Concomitant Medications

Prior and concomitant medications will be coded using WHO Drug Dictionary. Concomitant medications will be summarized as number and percentage of subjects.

For classifying study phase for concomitant medications, use the following definition.

Study Phase	Definition
Prior	If medication end date is not missing and is before date of first dose of study medication.
Concomitant	Any medication that is not a prior

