7.1.5. Study Period

Adverse events will be classified according to the time of occurrence relative to the study intervention period.

Treatment emergent	Definition
Y	If event start date is not missing and is before date of first dose of study medication.
N	Any event started on or after date of first dose of study medication or event date is missing or partial

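### SAP 5.3.2.1 and SAP 7.1.5 define treatment emergence in opposite ways, and as written neither puts follow-up adverse events into the summary table

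*SAP*

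**What the plan says.** SAP 5.3.2.1 (Adverse Events) opens the treatment-emergent (TEAE) window on the first infusion day and closes it with the words "on or before the last day of infusion treatment". Treatment AEs are summarised as subjects with an event, percentage and number of events, "whereas non-TEAEs are presented in listings". Individual AEs are also listed. On tables, the section adds: "The details of the planned displays are in programming specification document".

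SAP 7.1.5 (Study Period) has a two-row table headed as the treatment-emergent flag. The Y row reads: "If event start date is not missing and is before date of first dose of study medication". The N row reads: "Any event started on or after date of first dose of study medication or event date is missing or partial".

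SAP 7.1.3 defines a prior medication in nearly the same words as that Y row: "If medication end date is not missing and is before date of first dose of study medication".

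The protocol's Adverse Events section states that "the period of observation for collection of AEs extends from the time the patient gives informed consent through Week 26", or to the early discontinuation visit. Table 2 of the protocol schedules AE monitoring at Weeks 18, 22 and 26, and SAP 2.2 calls this period safety follow-up. Drug-related AEs and serious AEs (SAEs) are a secondary endpoint in the protocol and in SAP 2.1.

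**The concern.** Two sections of one SAP drive the same derivation and cannot both be followed. A program written from 7.1.5 as it stands would tabulate only events that began before any product was given. A program written from 5.3.2.1 would leave out every event that began after the last infusion day. That includes an event starting the day after Infusion 5, which the protocol's 24-hour telephone call is there to detect.

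The phrase about the last day of infusion treatment is also undefined. It most naturally means each patient's own last infusion, though SAP 2.2's planned 14-week treatment period is a possible reading. Under the first reading, a patient who stops infusions but is followed to Week 26 (Protocol, Withdrawal, Removal, and Replacement of Patients) stays in the safety set with a shortened window. A delayed reaction that starts after an infusion day and ends treatment would then not be a TEAE.

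The count-and-percentage table is the only AE summary that the SAP text describes. In a single-arm study without hypothesis tests, it is a core safety output. If the drug-related AE/SAE endpoint is drawn from TEAEs, it is under-counted; the SAP does not say which events feed it.

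**Working it through.** The plan states no figure to reproduce, so the check applies each rule to every possible onset day.

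**Inputs.** Day 1 is the first infusion day and there is no Day 0 (SAP 7.1.6). Screening lasts up to 14 days, infusions fall at Weeks 0, 2, 6, 10 and 14, and the study ends at Week 26 (SAP 2.2). Visit windows are ±3 days (Protocol, Table 2). At nominal timing:

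- Infusion 5: 14 × 7 + 1 = Day 99
- Week 26: 26 × 7 + 1 = Day 183

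**Classification by onset**

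| Onset | SAP 5.3.2.1 | SAP 7.1.5 as written | SAP 7.1.5, flags swapped |
|---|---|---|---|
| Day −14 to −1 (14 days) | no | Y | N |
| Day 1 to 99 (99 days) | yes | N | Y |
| Day 100 to 183 (84 days) | no | N | Y |
| Missing or partial date | no rule | N | Y |

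One rule needs onset on or after first dose and the other needs onset before it, so the overlap of the two as written is empty. Days 100 to 183 are treatment emergent under neither. After a swap, the sections agree on Days 1 to 99 and disagree on Days 100 to 183.

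**Time excluded by 5.3.2.1 for a patient with all five infusions**

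- Nominal: 183 − 99 = 84 days; 84/183 = 45.9%
- Latest Infusion 5, earliest Week 26: 180 − 102 = 78 days; 78/180 = 43.3%
- Earliest Infusion 5, latest Week 26: 186 − 96 = 90 days; 90/186 = 48.4%

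**Patients who stop early but are followed to Week 26**, if the window ends at their own last infusion:

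| Infusions received | Last infusion day | Days excluded | Share of 183 |
|---|---|---|---|
| 4 | 71 | 112 | 61.2% |
| 3 | 43 | 140 | 76.5% |
| 2 | 15 | 168 | 91.8% |
| 1 | 1 | 182 | 99.5% |

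If the window ends with the planned treatment period, the figure is 84 days (45.9%) for all of them. The documents do not say how many such patients to expect.

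**From time to events (by assumption).** The documents give no AE rates. Let r be the follow-up AE rate divided by the treatment-period rate. For a patient with all five infusions, the share of events lost is 84r/(99 + 84r): 17.5%, 29.8%, 45.9% and 62.9% for r = 0.25, 0.5, 1 and 2.

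The number of subjects with at least one event falls proportionally less. With Poisson events averaging m per subject over Days 1 to 99, the fall is 1 − (1 − e^(−m))/(1 − e^(−m(1 + 84r/99))). At m = 1 and r = 1, the table would show 63.2% of subjects instead of 84.3%, a fall of 25.0%. For m from 0.5 to 2 and r from 0.25 to 2, the fall runs from 5.1% to 46.9%.

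**The case against.** The strongest reply is that 7.1.5 contains an evident slip. A Y for treatment emergence on events before first dose has one sensible reading, and the wording echoes the prior-medication rule. SAP 5.3.2.1, the main analysis text, has the start condition right, and 7.1.5 sits under supporting documentation. A table of pre-dose events only would probably be nearly empty and be noticed, since Table 2 schedules no AE monitoring at screening. All of this is fair, and 0 of 183 is an unlikely outcome in practice. But the SAP states no order of precedence, and correcting the slip leaves the sections disagreeing on when the window ends.

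It can also be said that a swapped 7.1.5 would fill a gap on missing dates instead of creating a conflict. That stands: 5.3.2.1 has no such rule.

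Next, the effect on the secondary endpoint is conditional. That endpoint is not limited to TEAEs, SAP 5.4 says the analysis follows the protocol, and SAP 1 says that "specification of the data displays will be provided in the Programming Specifications (PS) document". That document is not available, so an additional all-AE or SAE table cannot be ruled out. This limits the consequence. It does not remove the fault, because what is deferred is the displays, and the conflict lies in the SAP's own definitions.

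Finally, every AE is still listed, the study has 55 patients, and window length alone would be a lesser point in a single-arm study with no test. The rate illustrations reflect chosen inputs and are not bounds. The use of TAE beside TEAE is only terminology. These points all stand.

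**Conclusion.** The concern holds. As written, no event is treatment emergent under both sections, and AEs starting after the last infusion day are treatment emergent under neither. Reversing the 7.1.5 flags mends the start of the window but not its end.

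The firm measure is 84 of 183 nominal post-dose days (45.9%; 43.3% to 48.4% with the visit windows) outside the 5.3.2.1 summary for a patient with all five infusions. The share is larger for early stoppers if the window ends at their own last infusion. These are shares of time at scheduled timing; the share of AEs lost is unknown.

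The weight of the point rests on the contradiction and the inverted flags. Data capture, the individual listings and the study stopping rules are not affected. COVID-19 symptoms and hospitalizations, respiratory infections, laboratory data, vital signs and examinations have their own summaries in the SAP. The conclusion reads the undefined TAE as TEAE, which the contrast with non-TEAEs in the same sentence supports.

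**What to change.** - Put one definition in 5.3.2.1 and 7.1.5: onset on or after the first infusion, through the Week 26 or early discontinuation visit.
- Correct the Y and N rows in 7.1.5 to match.
- Class an event with a missing or partial date as treatment emergent unless the known date parts show onset before first dose.
- State that drug-related AEs and SAEs are tabulated over this window.
- Use a single defined term in place of TEAE and TAE.
- Optionally, show treatment and follow-up as two columns with a total.

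If the sponsor prefers a shorter window, it should define the last day of infusion treatment and give later-onset AEs their own table of subjects, percentages and events.

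The cost is wording in two SAP sections and one derivation, with the programming specification and the related-AE/SAE tables brought into line. No new data are needed. Under the single Week 26 definition, tabulated AE counts can only stay the same or rise relative to 5.3.2.1.

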5.3.2.2. Clinical Laboratory data

Laboratory evaluations including the analyses of Biochemistry laboratory tests, Hematology laboratory tests and Urinalysis. The details of the planned displays are in programming specification document.

All laboratory parameters, including numerical urine analysis parameters will be summarised descriptively. Categorical urine analysis results will be summarized using count and percentage based on subjects.

Data recorded at unscheduled assessments will not be included in tables and figures but will be listed.

5.3.3. Additional Safety Assessments

The analyses of non-laboratory safety test results including physical examination and vital signs.

Physical Examination and Vital signs will be summarized using count and percentage based on subjects. The vital signs based on visit and change from baseline will be summarized using descriptive statistics.

Individual Vital signs, Physical Examination evaluations will be listed.

The details of the planned displays are in programming specification document.

5.4. Changes to Protocol Defined Analyses

Analysis is planned as per protocol. No deviation from the planned protocol specified analysis.

6. SAMPLE SIZE

Sample size for this study is 55 patients.

7. SUPPORTING DOCUMENTATION

7.1. Study Population Analyses

Unless otherwise specified, the study population analyses will be based on the “Safety” population. Screen failures will be summarized or listed based on the “Screened” population. A summary of the number of participants in each of the participant level analysis set will be provided.

7.1.1. Subject Disposition

A summary of the number and percentage of subjects who completed the study as well as those who withdrawn from the study will be provided by treatment. Reason of study withdrawn will be summarized by treatment.

A summary of the study intervention status will be provided. This display will show the number and percentage of subjects who have completed the Week 26, as well as primary reasons for withdrawn.

The study analysis set will be summarised in the subject disposition table.

The details of the planned displays are in programming specification document.

7.1.2. Demographic and Baseline Characteristics

The demographic characteristics including, age, sex, ethnicity, race, height at baseline, weight at baseline, BMI at baseline will be summarized with descriptive statistics. In addition, the following categories will be summarized: 18-64, 65-84 and >=85 based on the safety analysis set.

Listings of demographic characteristics will also be produced.

The details of the planned displays are in programming specification document.

7.1.3. Prior and Concomitant Medications

Prior and concomitant medications will be coded using WHO Drug Dictionary. Concomitant medications will be summarized as number and percentage of subjects.

For classifying study phase for concomitant medications, use the following definition.

Study Phase	Definition
Prior	If medication end date is not missing and is before date of first dose of study medication.
Concomitant	Any medication that is not a prior

7.1.4. Criteria for Potential Clinical Importance

The potential clinical importance criteria are not defined for this trial.

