- Monitor for AEs. Observe the patient for at least 1 hours after infusion for symptoms of infusion-related reactions and allergic reactions, including anaphylaxis (See Appendix 1).
- Instruct the patient on recognition of delayed serious allergic reactions, including anaphylaxis and seeking for medical assistance.
- Telephone encounter 24 hours after the infusion will be performed to assess the occurrence of AEs.

Follow Up Weeks 18, and 22.

- Weight will be measured
- Vital Signs will be measured.
- Concomitant medications will be reviewed and updated if necessary.
- Medical History will be reviewed and updated if necessary. If the patient reported a medication which does not match the current medical history, further investigation will be required to determine whether it was an Adverse Event, or the patient just forgot to mention it before. If it is found to be an AE, it should be recorded in the appropriate CRF. If the patient forgot to mention it before, a note to file (NTF) should be made to clarify the case.
- Physical examination performed by principal investigator or sub-investigator.

Weeks 26 (End of the Study or Early Discontinuation Visit)

- Weight will be measured
- Vital Signs will be measured.
- Concomitant medications will be reviewed and updated if necessary.

- Medical History will be reviewed and updated if necessary. If the patient reported a medication which does not match the current medical history, further investigation will be required to determine whether it was an Adverse Event, or the patient just forgot to mention it before. If it is found to be an AE, it should be recorded in the appropriate CRF. If the patient forgot to mention it before, a note to file (NTF) should be made to clarify the case.
- Blood samples will be collected.
- Physical examination performed by principal investigator or sub-investigator.

If a patient prematurely withdraws from the study for any reason, the early discontinuation visit requirements should be completed. If the early discontinuation visit is not done, the reason(s) will be recorded in the CRF.

Unscheduled Visits

The Investigator may at his/her discretion arrange for a patient to have an unscheduled assessment, especially in the case of adverse events (AEs) that require follow-up, or an AE considered by the Investigator to be possibly related to the use of the investigational product. The unscheduled visit page in the CRF must be completed.

Efficacy Assessments

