Vital signs (body temperature, pulse, oxygen saturation, systolic and diastolic blood pressure measurements) will be evaluated at the visits indicated in the schedule of assessments. It is important that all vital signs be measured after the patient has been resting in a sitting position for at least 5 minutes. Blood pressure measurements are to be taken in the same arm for the duration of the study. Body weight (without coats and shoes) will be recorded whenever vital signs are recorded, and height (without shoes) will be recorded at Infusion 1 (baseline) only.

Vital sign measurements will be repeated if clinically significant or machine/equipment errors occur. Out-of-range blood pressure and pulse measurements will be repeated at the Investigator's discretion. Any confirmed, clinically significant vital sign measurements will be recorded as AEs and followed up as such.

Physical Examination

A complete physical examination (head, eyes, ears, nose, throat, heart, lungs, abdomen, skin, cervical and axillary lymph nodes, neurological, and musculoskeletal systems) will be performed at Infusion 1 (Baseline).

A limited physical examination to verify continued patient eligibility and to follow up any change in medical history will be performed at the visits indicated in the schedule of assessments. Symptom-driven physical examinations will be performed as clinically indicated at any study visit. All changes not present at baseline or described in the past medical history and identified as clinically noteworthy will be recorded as AEs.

Clinical Laboratory Parameters

The Investigator must review all laboratory reports and document the review. Any laboratory test result or change considered by the Investigator to be clinically significant should be considered an AE and recorded in the AE CRF. Clinically significant abnormal values occurring during the study will be followed until repeat test results return to normal, stabilize, or are no longer clinically significant.

Laboratory tests to be performed during the study:

Complete Blood Count with Differential	Il-10
Chemistry	IL-6
Coagulation study (PTT/PT/INR)	Tumor Necrosis Factor alpha
C Reactive Protein	Rapid Antibody Test COVID-19

Adverse Events

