2. SUMMARY OF KEY PROTOCOL INFORMATION

2.1. Study Objective(s), Estimand(s) and Endpoint(s)

Objectives	Endpoints
Primary Objective	Primary Endpoint

 To investigate the efficacy of HB-adMSCs in providing immune support against development of Coronavirus Disease by incidence of hospitalization for COVID-19, incidence of symptoms associated with COVID-19 (ie., fever, shortness of breath/difficulty breathing, and/or cough), and severity of COVID-19 associated symptoms ((fever 38C or higher, cough, shortness of breath/difficulty breathing). 	
 Incidence of hospitalization for COVID-19. Incidence of symptoms associated with COVID-19
Secondary Objective	Secondary Endpoint

 To investigate the efficacy of HB-adMSCs in the prevention of upper and lower respiratory infections in a high-risk population. 	
 Absence of upper/lower respiratory infections (with hospitalization criteria) up to 3 months post infusions. Change from baseline in leukocyte differential Change from baseline in C-Reactive Protein Change from baseline in TNF-alpha Change from baseline in IL-6 Change from baseline in IL-10

CONFIDENTIAL**Hope Biosciences****HBCOV01**

Objectives	Endpoints
	
• Clinically significant changes in laboratory values, vital signs, weight, and physical examination results.• Incidence of Adverse Events (AEs) and serious AEs (SAEs) related to the drug

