7.1.7. Assessment Window

For data summaries by visit, scheduled visits with nominal visit description will be displayed. Unscheduled visits will not be displayed or slotted into a visit window. While in the baseline derivation or post-baseline worst scenarios are derived, unscheduled visits are considered. All unscheduled visits will be displayed in listings, as appropriate.

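### The secondary endpoint on clinically significant changes has no dedicated summary in the SAP, and the adverse-event tables that could stand in for it close at the last infusion

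*SAP*

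**What the plan says.** SAP 2.1, repeating the protocol's Study Endpoints, lists as a secondary endpoint "Clinically significant changes in laboratory values, vital signs, weight, and physical examination results". SAP 7.1.4 then states: "The potential clinical importance criteria are not defined for this trial".

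The protocol supplies a working definition by investigator judgement. Under Clinical Laboratory Parameters: "Any laboratory test result or change considered by the Investigator to be clinically significant should be considered an AE and recorded in the AE CRF". Under Vital Signs, Height, and Weight: "Any confirmed, clinically significant vital sign measurements will be recorded as AEs and followed up as such". Its Physical Examination section likewise sends new, clinically noteworthy findings to the AE record. AEs are collected from consent to Week 26.

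In the SAP, 5.3.2.1 defines a treatment-emergent event as one starting on or after the first infusion day and "on or before the last day of infusion treatment". Treatment-emergent events are tabulated and all others are listed. Section 7.1.5 gives a second definition: Y for an event that starts before the first dose, N for one that starts on or after it or whose date is missing or partial.

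On unscheduled data, SAP 5.3.2.2 says: "Data recorded at unscheduled assessments will not be included in tables and figures but will be listed". SAP 7.1.7 keeps unscheduled visits out of by-visit displays, but where "post-baseline worst scenarios are derived, unscheduled visits are considered". SAP 5.4 reports no departure from the protocol's analyses.

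**The concern.** The other secondary endpoints each have a stated analysis: the leukocyte differential, CRP, the cytokines and respiratory infection in SAP 5.3.1, and AEs in 5.3.2.1. This one does not. No planned table says how many subjects had at least one clinically significant change in each domain.

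The AE tables are the natural substitute, but they do not cover the whole follow-up, they are not split by the endpoint's four domains, and two SAP sections define their scope in opposite ways. At stake is a named safety endpoint in a single-arm study of 55 subjects, where one or two affected subjects matter and there is no control group against which to read an incomplete count. A programmer who follows the SAP as written would produce tables that leave out significant findings arising during follow-up.

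**Working it through.** The plan gives no figure for this endpoint, so there is none to reproduce. The check follows each domain from the protocol's recording rule to the SAP's displays, then counts what falls after the last infusion.

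**Step 1. Domain by domain**

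| Domain | Protocol rule for recording as an AE | SAP summary outside the AE tables |
|---|---|---|
| Laboratory | Yes, investigator-judged | Descriptive statistics; unscheduled results listed only (5.3.2.2) |
| Vital signs | Yes, if confirmed and significant | By visit and change from baseline; counts and percentages with no categories stated (5.3.3) |
| Physical examination | Yes, if new and noteworthy | Counts and percentages with no categories stated (5.3.3) |
| Weight | No specific rule | Named only at baseline (7.1.2); otherwise only the general by-visit rule (5.1.1) |

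No row ends in a stated count of subjects with a clinically significant change.

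**Step 2. The AE route under SAP 5.3.2.1**

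Inputs, from protocol Table 2: infusions at Weeks 0, 2, 6, 10 and 14; laboratory draws at Weeks 0, 6, 14 and 26; vital signs, weight and examination at Weeks 0, 2, 6, 10, 14, 18, 22 and 26; every visit ± 3 days. Baseline assessments precede the first infusion.

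- Follow-up after the last infusion: 26 − 14 = 12 weeks, and 12/26 = 46%.
- Effect of the visit windows, in days from first infusion (Week 14 = 98, Week 26 = 182): longest (185 − 95)/185 = 49%; shortest (179 − 101)/179 = 44%.
- Post-baseline laboratory draws are Weeks 6, 14 and 26. Only Week 26 is later than Week 14: 1 of 3.
- Post-baseline vital-sign, weight and examination visits are Weeks 2, 6, 10, 14, 18, 22 and 26. Weeks 18, 22 and 26 are later: 3 of 7.

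So 2 of 3 draws and 4 of 7 visits can still feed the AE tables, provided that onset is dated to the visit day. A Week 14 result dated to the day it was reported would fall outside.

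The window is set by each subject's own last infusion. The protocol follows subjects who stop infusions to Week 26 if they keep their consent. For one whose last infusion was at Week 6, 26 − 6 = 20 of 26 weeks lie outside, with 2 of 3 draws and 5 of 7 visits.

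**Step 3. The AE route under SAP 7.1.5**

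Every event on or after the first dose is coded N. Read literally, none of the 3 draws or 7 visits can yield a treatment-emergent event, and only events before the first dose would be tabulated. This cannot be reconciled with 5.3.2.1.

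**Step 4. Unscheduled data**

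The protocol's Unscheduled Visits section provides for such visits "especially in the case of adverse events (AEs) that require follow-up". SAP 5.3.2.2 and 7.1.7 agree that these data stay out of by-visit displays. They part only over a worst-value table: 7.1.7 would count unscheduled results in it, and 5.3.2.2 bars them from any table. The SAP names no such table, so the clash is latent.

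**The case against.** The strongest reply is that the endpoint already has both a definition and a route to results. Significance is the investigator's judgement, three of the four domains go to the AE form, 5.3.2.1 tabulates events through the last infusion, and every AE is listed. SAP 7.1.4 speaks of potential clinical importance criteria, which need not cancel that judgement. Display details are deferred to a programming specification that is not among the documents, so a table may be planned there.

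Much of this stands, and it rules out several stronger readings that a reader might infer:

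- *That the endpoint gets no result.* Significant laboratory, vital-sign and examination findings up to the last infusion can reach the AE tables under 5.3.2.1. Later ones are listed, and 5.3.3 adds counts and percentages.
- *That means will hide the extreme values.* SAP 5.1.1 also reports the median, minimum and maximum at each visit, so extreme scheduled values appear, including at Week 26.
- *That 5.3.2.2 and 7.1.7 conflict outright.* They agree on by-visit displays, as Step 4 shows.
- *That unscheduled repeats are the most abnormal values.* Nothing in the documents supports this. Abnormal results are followed until they normalise, stabilise or cease to matter clinically, so a repeat may be the more normal value.

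What the reply does not meet is the cut-off in the AE tables, the reversed flag in 7.1.5, the gap for weight and the lack of any count by domain. The programming specification could add a display. But how a named secondary endpoint is summarised belongs in the SAP, and 7.1.4 says that criteria are undefined, not that they are given elsewhere.

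**Conclusion.** Wrong as written, and it should be changed. The SAP has no dedicated summary for a named secondary endpoint, and its own rules keep the AE tables from filling the gap. Under 5.3.2.1, AEs starting in the last 12 of 26 nominal weeks (46%; 44% to 49% with the visit windows) are listed only. That period holds 1 of 3 post-baseline laboratory draws and 3 of 7 post-baseline vital-sign, weight and examination visits. Under 7.1.5 read literally, no post-dose event is tabulated as treatment emergent. Weight lacks both a named post-baseline analysis and a specific AE-recording rule.

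The defect is incomplete tabulation, not lost data: AEs are collected and listed through Week 26. The figures assume all five infusions on the nominal schedule, with onset dated to the visit. They are shares of follow-up time and of visits, not forecasts of how many events would be missed, for which the documents give no basis. No sample-size figure or hypothesis test is affected, because SAP section 3 plans no test.

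**What to change.** 1. In SAP 5.3.2.2 and 5.3.3, state that clinical significance is judged by the investigator. Add n (%) of safety-set subjects with at least one clinically significant post-baseline change, by domain (laboratory, vital signs, weight, physical examination), through Week 26, counting scheduled and unscheduled assessments. Name the data source for weight. Word 7.1.4 to agree.
2. Limit the exclusion of unscheduled data in 5.3.2.2 to by-visit tables and figures, so that it agrees with 7.1.7.
3. Replace the definitions in 5.3.2.1 and 7.1.5 with a single one, and tabulate AEs with onset from the first infusion through Week 26.

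Baseline-to-worst laboratory shift tables would be a useful addition but are optional.

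The cost is SAP wording and a few more tables. Laboratory, vital-sign and examination findings need no new data collection, because the protocol already sends the investigator's judgement to the AE record; only weight needs a stated source. The downside is that more abnormal findings appear in the report, with no control group to set them against.
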